6.2.7.1 ARIA-E

6.2.7.1.1 *Event Definition*

An event of ARIA-E is defined as an MRI scan where the Brain MRI Worksheet (BMW) shows the presence of vasogenic edema.

6.2.7.1.2 *Severity Definition*

ARIA-E severity is based on radiographic severity as captured on BMWs.

6.2.7.1.3 *Resolution and Time to Resolution Definition*

- ARIA-E is considered resolved for a participant if all the subsequent MRI scans showed no ARIA-E following the last MRI scan showing ARIA-E.
- Time to resolution is defined as the number of days from the exam date of the first MRI scan showing ARIA-E to the exam date of the earliest MRI showing no ARIA-E after the last one showing ARIA-E. If a participant had a resolved but recurrent ARIA-E after the previous one was resolved, both times to resolution are included.
- If there is existing ARIA-E at LTE Baseline, it is not included as a new occurrence during LTE.

6.2.7.1.4 *Time to First Occurrence and Recurrence Definition*

- Time to the first occurrence is defined as the number of days from the first dose date in the LTE Study to the exam date of the first new MRI scan showing ARIA-E.
- For a participant, if there was an MRI scan showing ARIA-E, followed by a subsequent MRI scan not showing ARIA-E, followed by a subsequent MRI scan again showing ARIA-E, this participant is considered to have a reoccurrence of ARIA-E.

6.2.7.2 **ARIA-H**

For the MRI scans collected in the Core Study, the definitions are specified in the Core Study SAP. Definitions below are for the MRI scans collected in the LTE Study.

6.2.7.2.1 *Event Definition*

For the MRI scans collected in the LTE Study, an event of new ARIA-H is defined as an MRI scan at a post-LTE Baseline visit if the overall ARIA-H radiographic severity is Mild, Moderate or Severe as captured on BMWs.

6.2.7.2.2 *Severity Definition*

For the MRI scans collected in the LTE Study, new ARIA-H overall severity and individual component severity are based on the radiographic severity as captured on BMWs.

6.2.7.2.3 *Time to First Occurrence Definition*

Definition is the same as the time to first occurrence definition for ARIA-E.

6.2.8 **Neurological Examination**

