7. STATISTICAL ANALYSIS

7.1 General Data Handling Rules and Definitions

“AL002 40 and 60 mg/kg combined group” refers to the group pooling AL002 40 mg/kg and 60 mg/kg treatment groups. And “AL002 total” refers to the group pooling AL002 15 mg/kg, 40 mg/kg, and 60 mg/kg, and the TC treatment groups.

Assessments collected in the Core and LTE Study that will be provided in by-participant data listings are specified in each respective section. If any dosed participant is found to not have valid documented informed consent, that participant’s data will be excluded from the report, except as necessary to document the error. By-participant data listings will be presented for data collected in the Core and LTE Study for all participants and sorted by treatment group, participant identification (ID) number, visit date, and time (if applicable), unless otherwise specified. Data collected on log forms, such as AEs, will be presented in chronological order for each participant. Age at time of informed consent in the LTE Study, sex at birth, race, and ethnicity will be included in the listings.

Analyses (including analysis sets that analyses will be conducted on) to be performed for each interim analysis (IA) are specified in Section 8.

All analyses will be conducted using SAS® version 9.4 or later.

Except where specified, all continuous variables will be summarized with descriptive statistics (the number of non-missing values, mean, standard deviation (SD), median, 25% quartile (Q1), 75% quartile (Q3), minimum (min) and maximum (max)) and all categorical variables will be summarized with frequency counts and percentages, by treatment group.

Missing data will be assumed as missing at random (MAR) for all analyses and will not be imputed, unless otherwise specified.

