7.4.8 Magnetic Resonance Imaging (MRI) for ARIA-E and ARIA-H Events

Incidence of the occurrence of ARIA-E within each post-baseline visit will be summarized by radiographic severity for each visit (refer to [Table 7-12](#) and [Table 7-13](#) for analysis visit window definitions) and overall. The same incidence table will be summarized for ARIA-H. In addition to radiographic severity for ARIA-H, individual radiographic severity for microhemorrhages, leptomeningeal hemosiderosis, and macrohemorrhages for the occurrence of ARIA-H will also be summarized by visit and overall.

In the case of multiple values in the baseline analysis visit window, the rules described in the Section [7.1.3.2](#) still apply. In the case of multiple values in a post-baseline analysis visit window, the rules described in the Section [7.1.3.2](#) do not apply to this summary, but the worst-case scenario will be applied as below:

- A participant having a record indicating no ARIA-E and a different record indicating ARIA-E is considered experienced ARIA-E per visit or overall.
- A participant having experienced ARIA-E more than once per visit or overall is counted once in the number of participants with ARIA-E per visit or overall.
- The maximum severity is selected if ARIA-E was observed more than once for a participant per visit or overall post-baseline.

The same rules described above also apply to ARIA-H. In addition, the maximum severity of ARIA-H is selected for a participant per visit or overall post-baseline, and the individual radiographic severity corresponding to the selected ARIA-H will be summarized per visit or overall post-baseline.

APOE genotype, time to the first occurrence, resolution, time to resolution, and reoccurrence will be summarized for participants with ARIA-E. APOE genotype and time to the first occurrence will be summarized for participants with post-baseline ARIA-H.

The number and percentage of participants who had post-baseline ARIA-E but did not have ARIA-H any time post-baseline will be summarized. The number and percentage of participants who had ARIA-H but did not have ARIA-E any time post-baseline will be summarized. Similarly, the number and percentage of participants who had ARIA-H and ARIA-E any time post-baseline will be summarized.

Overall incidence of the occurrence of ARIA-E and ARIA-H will also be summarized by APOE genotype.

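### SAP 6.2.7.1.3 gives conflicting rules for ARIA-E time to resolution when ARIA-E recurs, and SAP 7.4.8 has no censoring rule for episodes that have not resolved

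*SAP*

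**What the plan says.** SAP section 6.2.7.1.3 contains three rules that matter here.

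- **Status.** "ARIA-E is considered resolved for a participant if all the subsequent MRI scans showed no ARIA-E following the last MRI scan showing ARIA-E". This rule works per participant and is keyed to the last positive scan.
- **Duration.** Time to resolution runs "from the exam date of the first MRI scan showing ARIA-E to the exam date of the earliest MRI showing no ARIA-E", where that clear scan must come later than the participant's final positive scan.
- **Recurrence.** "If a participant had a resolved but recurrent ARIA-E after the previous one was resolved, both times to resolution are included".

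Section 6.2.7.1.4 recognises a reoccurrence when a positive scan is "followed by a subsequent MRI scan not showing ARIA-E, followed by a subsequent MRI scan again showing ARIA-E". Section 6.2.7 confines these definitions to the LTE Analysis. The Integrated Analysis takes its definitions from the Core Study SAP, which is not among the documents supplied.

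On reporting, section 7.4.8 says that "time to the first occurrence, resolution, time to resolution, and reoccurrence will be summarized for participants with ARIA-E". It gives no rule for an episode still open at the last scan. The general default in section 7.1 is that "all continuous variables will be summarized with descriptive statistics (the number of non-missing values, mean, standard deviation (SD), median" and further order statistics are given, with no imputation of missing data. For time to first occurrence, section 7.4.8 does specify Kaplan-Meier curves with a censoring date. It also says that the full set of MRI summaries belongs to the Integrated Analysis, and that the LTE Analysis provides just the overall ARIA summary.

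**The concern.** The duration rule runs from the first positive scan to the clear scan after the last one. For a participant whose ARIA-E clears and returns, that is a single interval containing episode one, the clear gap and episode two. The recurrence rule asks for two times. The status rule makes the recurrence rule harder to apply: a first episode followed by another positive scan is not resolved under it, so a resolved but recurrent case cannot arise. Two competent programmers could produce different tables from the same scans.

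The second weakness is separate. An open episode has no clearing date, hence no value, and the defaults summarise only non-missing values. Open episodes tend to be the long ones, so leaving them out pulls the duration statistics down.

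What is at stake is a descriptive safety statement: how long ARIA-E lasts in participants who develop it. The effect of titration on ARIA is a primary objective, so this figure would be read beside the incidence and severity results. Recurrence is foreseen, because protocol Table 8 has its own row for a second ARIA-E after full resolution.

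**Working it through.** The plan states no numeric time to resolution, so there is no figure to reproduce. The check has two parts.

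**1. Literal formula against per-episode durations**

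Let e1 and e2 be the first positive scans of two episodes, and c1 and c2 the first clear scans after each.

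- Literal span = c2 − e1
- Per-episode durations = c1 − e1 and c2 − e2
- Clear time counted by the literal span = e2 − c1

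Example on the MRI target days of SAP Table 7-13, with any unscheduled scans consistent with this pattern: positive Day 57, clear Day 113, positive Day 225, clear Day 281.

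- Literal: 281 − 57 = 224 days
- Per episode: 113 − 57 = 56 and 281 − 225 = 56 days
- Clear gap included: 225 − 113 = 112 days, and 56 + 112 + 56 = 224

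If the Day 281 scan is still positive at the data cutoff, the status rule calls the participant unresolved and the formula returns no value. The completed 56-day first episode then disappears as well.

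Varying the assumption: episodes are detected at Days 57 and 169, follow-up scans come every 28, 35 or 42 days (the protocol asks for every 4 to 6 weeks), and each episode clears at its first or second follow-up scan.

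| Scan interval (days) | Clears at scan | Per episode (days) | Literal span (days) | Clear gap counted (days) |
|---|---|---|---|---|
| 28 | first | 28, 28 | 140 | 84 |
| 35 | first | 35, 35 | 147 | 77 |
| 42 | first | 42, 42 | 154 | 70 |
| 28 | second | 56, 56 | 168 | 56 |
| 35 | second | 70, 70 | 182 | 42 |
| 42 | second | 84, 84 | 196 | 28 |

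The literal span is between 196/84 = 2.3 and 140/28 = 5 times each episode's duration.

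**2. Effect of leaving out unresolved episodes**

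The documents give neither a duration distribution nor an unresolved share, so these inputs are assumptions: true median 84 days, Weibull shape 1 or 2, scans every 35 days, and censoring uniform from 0 to 2000, 800, 400 or 250 days and independent of duration. There were 100,000 simulated episodes per setting. On the scan grid the full-data median is 105 days (84 rounded up to the next multiple of 35).

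| Shape | Unresolved | Median, all → resolved only (days) | Mean, all → resolved only (days) | Change in mean |
|---|---|---|---|---|
| 1 | 7% | 105 → 105 | 139.4 → 131.4 | −6% |
| 1 | 18% | 105 → 105 | 139.4 → 117.4 | −16% |
| 1 | 33% | 105 → 70 | 139.4 → 94.8 | −32% |
| 1 | 49% | 105 → 70 | 139.4 → 74.9 | −46% |
| 2 | 5% | 105 → 105 | 107.0 → 105.8 | −1% |
| 2 | 13% | 105 → 105 | 107.0 → 103.7 | −3% |
| 2 | 27% | 105 → 105 | 107.0 → 99.4 | −7% |
| 2 | 43% | 105 → 70 | 107.0 → 91.3 | −15% |

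The Kaplan-Meier median, with unresolved episodes censored, was 105 days in all eight settings.

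**The case against.** Several points on the other side stand.

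- **Scope.** The definition governs the LTE Analysis, for which section 7.4.8 promises only an overall ARIA summary. It is not certain that the formula feeds any table. The Integrated Analysis uses a definition that cannot be checked here, and the Core Study SAP might also contain a censoring rule.
- **Intent.** The recurrence sentence points to an episode-level reading. A programmer who follows it and reads the duration formula per occurrence gets 56 and 56 days. A reader might infer that recurrent durations will be overstated; the documents support that only if the formula is programmed literally.
- **Unresolved cases.** A reader might infer that the SAP instructs their exclusion. It does not. The omission follows from the missing censoring rule plus the general defaults. Resolution is summarised alongside and all MRI findings are listed, so these cases remain visible.
- **Likely size.** The protocol calls for scans every 4 to 6 weeks until ARIA-E resolves, and section 3.2.5 defers the ET Visit until an adverse event behind withdrawal has resolved. Both make a large unresolved share less plausible at the final analysis. The protection is incomplete: the same section also sets a 4-to-8-week limit for the ET Visit and lets follow-up end at stabilisation, and interim cutoffs will catch open episodes.
- **Importance.** Time to resolution is not an endpoint or estimand in protocol Table 1 or SAP Table 2-1. Scanning and dosing follow each participant's own MRI report and protocol Table 8, not this statistic.

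What does not fall away is the conflict in the text. The formula has to be reinterpreted before it can yield two times, and the status rule has no episode-level form.

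**Conclusion.** The definition in section 6.2.7.1.3 conflicts with itself for recurrent ARIA-E and should be corrected. Programmed literally, it counts scan-clear time (224 days against 56 and 56 in the example; 2.3 to 5 times each episode's duration across the assumed patterns), and it loses a completed first episode when the second is open.

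The missing censoring rule is a separate gap whose size is unknown. Under the assumed distributions it is small at 5–18% unresolved: no shift in the median, and a mean lower by about 1–16%. It becomes material at 43–49%, where the median falls from 105 to 70 days. Between these, the median moved at 33% (shape 1) but not at 27% (shape 2). A heavy unresolved share is more plausible at an interim cutoff than at the final analysis.

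The documents do not support a claim that reported duration will be biased in a known direction. The literal formula lengthens it, omission of open episodes shortens it, and neither the recurrence rate nor the unresolved rate is given. Nor do they support any effect on the ARIA incidence comparison or on participant management.

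**What to change.** Amend section 6.2.7.1.3 and the matching text in 7.4.8:

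1. Define an episode as starting at the first positive scan after baseline or after a clear scan, and ending at the first later clear scan.
2. Determine resolution and duration per episode.
3. Summarise time to resolution of the first episode by Kaplan-Meier, censoring unresolved episodes at the last evaluable MRI. This assumes that censoring is unrelated to duration, so give the reasons for censoring.
4. Report the number of unresolved episodes and list recurrent episodes separately.
5. State whether the LTE Analysis reports time to resolution under section 7.4.8. If it does not, the definition can be removed.
6. Confirm that the Core Study SAP definition used for the Integrated Analysis matches, including its handling of open episodes.

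The cost is SAP wording and minor reprogramming. No new data are needed.

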6.2.10 Physical Examination (PE)

Complete PE includes evaluation of the head, eyes, ears, nose, and throat, and the cardiovascular, dermatological, musculoskeletal, respiratory, and gastrointestinal systems. Breast, rectal, and genitourinary exams are performed as clinically indicated.

Limited PE includes cardiovascular, respiratory, and gastrointestinal systems; further symptom-directed examination may also include any other pertinent system as required.

Abnormalities observed at baseline, as well as new or worsened clinically significant abnormalities at all other visits, will be recorded on the electronic CRF. New abnormal PE findings will be followed up at the next scheduled visit. New or worsened abnormalities should be recorded as AE on the AE electronic CRF if considered clinically significant in the Investigator's opinion.

6.2.11 Other Safety Assessments

6.2.11.1 Pregnancy Test

Serum pregnancy tests will be performed for all females of childbearing potential at scheduled visits (refer to the Schedules of Assessments in the protocols for scheduled visits).

6.3 Pharmacokinetic (PK) Endpoints

- Serum PK concentrations of AL002
- CSF PK concentrations of AL002 (when available)

6.4 Efficacy Endpoints and Estimands

6.4.1 Clinical Dementia Rating – Sum of Boxes (CDR-SB)

The Clinical Dementia Rating (CDR) is a global clinical scale with established diagnostic and severity-ranking utility widely used in clinical trials; one component of this scale is the CDR Sum of Boxes (CDR-SB). The CDR-SB is used in AD trials as a global measure of disease severity. The CDR-SB is rated based on participant and informant input. The CDR-SB assesses three domains of cognition (memory, orientation, judgment/problem solving) and three domains of function (community affairs, home/hobbies, personal care) using semi-structured interviews of both the study participant and a companion/informant carried out by a trained rater and scored using a standard methodology. Each domain is rated on a 5-point scale of functioning as follows: (0) no impairment; (0.5) questionable impairment; (1) mild impairment; (2) moderate impairment; (3) severe impairment (personal care is scored on a 4-point scale without a 0.5 rating available). Higher scores indicate greater impairment.

The CDR-SB score is a quantitative general index that provides more precision than the CDR-GS in participants with mild dementia. The CDR-SB score is obtained by summing all of the domain scores and the CDR-SB score ranges from 0 to 18.

If only one box (of 6) of the CDR-SB is missing, the sum of the boxes will be imputed by prorating the sum from the other 5 boxes as follows: the total from the remaining boxes will be multiplied by a factor that includes the maximum score for the missing boxes. For example, if the first box, "Memory" which ranges from a score of 0 through 3 (maximum = 3), is missing, then the multiplication factor = $18/(18 - 3)$

= 18/15 = 1.2. Thus, the total score for this example will be the sum of the remaining 5 boxes multiplied by 1.2. The imputed number will be rounded up to the nearest 0.5. If the score from more than 1 box is not available, the CDR-SB at that visit will be considered missing.

The interpretation of CDR-SB score is presented in [Table 6-2](#) (O’Bryant et al. 2010), with a higher score indicating a greater cognitive deficit.

Table 6-2 Dementia Severity Categories Based on CDR-SB Scores

| CDR-SB Range | Staging Category |
|--------------|-----------------------------------|
| 0 | Normal |
| 0.5 - 4.0 | Questionable cognitive impairment |
| 0.5 - 2.0 | Questionable impairment |
| 2.5 - 4.0 | Very mild dementia |
| 4.5 - 9.0 | Mild dementia |
| 9.5 - 15.5 | Moderate dementia |
| 16.0 - 18.0 | Severe dementia |

6.4.1.1 Main Estimand for Efficacy

- Treatment condition: Group T-T (AL002 15 mg/kg, 40 mg/kg or 60 mg/kg IV Q4W) continues their Core study treatment in the LTE Study; whereas Group P-TC treated with Placebo in the Core study will be titrated up to 60 mg/kg of AL002 in the LTE study.
- Target population: adult participants with AD excluding APOE e4/e4 participants.
- Efficacy endpoint: CFB in CDR-SB.
- Accounting for intercurrent events: a composite strategy will be used to handle intercurrent events as below:
 - Hypothetical strategy for handling premature study drug discontinuation for any reason (data will be considered missing after a participant prematurely discontinued study drug plus 37 days).
 - Treatment policy strategy for handling all other intercurrent events.
- Population-level summary: the percent reduction relative to placebo decline (the proportional treatment effect), comparing each dose level to placebo.

6.4.1.2 Supportive Estimand for Efficacy

The supportive estimand is defined with the same attributes as in the main estimand for efficacy, except that a treatment policy strategy will be used to handle all intercurrent events, except death. All on-study data will be included regardless of whether an intercurrent event occurs or not. The hypothetical strategy will be used for handling death.

Another supportive estimand for the primary efficacy endpoint is defined with the same attributes as the main estimand for efficacy, except that the population-level summary is the CFB in CDR-SB to Week 24, 48, 72 and 96, comparing each dose level to placebo.

6.4.2 Other Efficacy Endpoints

The other exploratory efficacy endpoints which apply to the main estimand for efficacy endpoints include:

- CFB in MMSE
- CFB in RBANS
- CFB in ADAS-Cog13
- CFB in ADCS-ADL-MCI
- CFB in ADCOMS
- CFB in modified iADRS.

6.4.2.1 Mini-Mental Status Examination (MMSE)

The MMSE (Folstein, Folstein, and McHugh 1975) is a brief test used to measure cognitive impairment with a lower score indicating a greater cognitive deficit. The total possible score of the MMSE is 30 points and it assesses orientation (time and place), registration, attention and calculation, recent memory, language (naming, comprehension, and repetition), and constructional praxis (copying a figure).

Missing MMSE items are considered missing not at random and in a study by Godin, Keefe, and Andrew 2017, those who were missing at least one item had lower levels of cognitive function compared to those who completed all items. If only 2 or fewer items (out of 11) are missing for the MMSE, the sum of non-missing raw score of all available items will be used as the MMSE score. If more than 2 items of the MMSE are not available, the MMSE at that visit will be considered missing.

6.4.2.2 Repeatable Battery for the Assessment of Neuropsychological Status (RBANS)

The RBANS used for this study is the updated version of the original RBANS (Randolph 2012) and is a collection of 12 subtests representing 5 neurocognitive domains: immediate memory, visuospatial/constructional, language, attention, and delayed memory. The raw scores from each subtest within a domain are converted to a summary score, or index score, for the domain by consulting normative data tables. Then the sum of index scores across the 5 domains is converted to a total scale that summarizes the participant's overall level of performance on this measure. The total scale score can range from 40 to 160 with a lower score indicating a greater cognitive deficit. The total scale score will be used for analysis. If any domain's index score is missing, then the total scale score will be missing.

6.4.2.3 Alzheimer's Disease Assessment Scale-Cognitive Subscale (ADAS-Cog13)

The ADAS-Cog13 includes 13 items assessing cognitive function with a higher score indicating a greater cognitive deficit. The instrument includes domains for memory, language, praxis, and orientation, as well as a number cancellation task and a delayed free recall task. The ADAS-Cog13 total score is defined as the sum of the individual 13 item scores, not including the individual Trials (Trials 1, 2 and 3) for the Word Recall Task.

For the ADAS-Cog13, if 4 or fewer of a total of 13 items are missing, the total score (maximum = 85) will be imputed as follows: the total from the remaining items will be multiplied by a factor that includes the maximum score for the missing items. For example, if the first item, "Word-Recall Task," which ranges from a score of 0 through 10 (maximum = 10), is missing, and the second item "Commands,"

which ranges from a score of 0 to 5 (maximum = 5), is missing, then the multiplication factor = $85 / (85 - (10 + 5)) = 85 / 70 = 1.21$. Thus, the total score for this example will be the sum of the remaining 11 items multiplied by 1.21. The imputed number will be rounded up to the nearest integer. If more than 4 items are missing, the total score of ADAS-Cog13 at that visit will be considered missing.

6.4.2.4 Alzheimer's Disease Cooperative Study – Activities of Daily Living – Mild Cognitive Impairment (ADCS-ADL-MCI)

The ADCS-ADL-MCI (Galasko et al. 1997) is a functional evaluation scale for MCI participants, based on the information provided by an informant/caregiver, that describes the performance of participants in several activities of daily living. It was adapted from the original ADCS/ADL scale, which was constructed to evaluate participants with dementia in the ADCS, as a measure of the AD participants' performance in ADL.

The ADCS-ADL-MCI is a multiple-choice questionnaire that clinicians may use to provide an assessment of mild cognitive impairment. It consists of 24 items, each answered "Yes", "No" or "Don't Know". If the respondent answers "Yes", there are sub questions that are either answered "Yes" or "No", rated on a numeric scale (which differs from question to question), or the respondent is asked to choose multiple items from a list. Only the first eighteen questions are included in the scoring.

The total score of ADCS-ADL-MCI is the summation of these response scales. The total score of ADCS-ADL-MCI ranges from 0 to 53, with a lower score indicating greater impairment.

For the ADCS-ADL-MCI, if 4 or fewer of a total of 18 items are missing, the total score will be imputed by a similar algorithm as that for the ADAS-Cog 13. The imputed value will be rounded up to the nearest integer. If more than 4 items are missing, the total score for ADCS-ADL-MCI at that visit will be considered missing. For each question, an answer of "No" or "Don't Know" will be coded to a value of 0 and is not considered as missing.

